2.1 General considerations

Descriptive statistics will include n (number of observations), mean, standard deviation, median, minimum and maximum for continuous variables, and frequencies and percentages for categorical variables.

The study eye is the eye identified by the investigator according to the protocol inclusion and exclusion criteria and recorded as such at the screening visit in the eCRF.

The efficacy analyses of this study will be based on the study eye data only.

For non-ocular, study eye, and fellow eye summary tables, figures, and listings will be based on all patients included in the analysis/set population under consideration. Unless otherwise specified, all confidence intervals (CIs) and p values will be two-sided and will be based on an alpha significance level of 0.05.

Central Reading Centre data will be used for efficacy summary tables and analyses, whilst all site and Central Reading Centre data will be included in listings.

2.2 Analysis sets

The following are common analysis sets used across the project.

Randomized Set: The Randomised Population will consist of all randomised patients.

Full Analysis Set (FAS): The Full Analysis Set (FAS) comprises all subjects randomised and whom have at least one post-baseline efficacy value for BCVA.

Safety Set: The Safety Set will consist of all patients who received at least one application of study treatment and had at least one post-baseline safety assessment. The statement that a patient had no adverse events also constitutes a safety assessment.

Per-Protocol Set: The Per-Protocol Set (PPS) will consist of all patients in the FAS who followed the treatment regimen as randomised and completed the study without clinically significant protocol deviations. Clinically significant protocol deviations will be identified and documented prior to the database lock. Refer to “Protocol Deviations” study document for further details.¹

In order to derive the analysis set, protocol deviations (defined prior to DB lock; impact on analysis defined in this document) and non-protocol deviations (based on the definition of the analysis set/according to this document) need to be considered.

The protocol deviations are mainly used in excluding entire patients or particular data within a patient from the Per Protocol Set (PPS) and are described in the Protocol Deviation Plan. Furthermore - to derive the analysis sets, non-protocol deviations will be used. Table 2-1 Analysis set exclusion summary below gives a summary of the non-protocol deviations that exclude patients from each analysis set.

Table 2-1 Analysis set exclusion summary

Analysis Set (to be excluded from)	Non-Protocol Deviations
Full Analysis Set	Not in the Randomized set Did not have at least one post-baseline efficacy value for BCVA
Per Protocol Set	Not in FAS Clinically significant protocol deviation(s)
Safety Set	Did not receive at least one study treatment Did not record at least one post-baseline safety assessment

All efficacy evaluations will be carried out on the FAS. The analysis for the primary efficacy evaluation will be carried out on both the FAS and the PPS population. Analyses for secondary and exploratory evaluations will be carried out on the FAS, and may also be carried out on the PPS population as part of sensitivity analyses. Within the FAS and PPS, patients will be analysed as randomised.

All safety evaluations will be carried out on the Safety set. Within the safety set, patients will be analysed as treated.

The number and percentage of patients in each analysis set will be summarized based on all patients included in the analysis set.

In addition, a listing will be produced to show the patient inclusion/exclusion into each of the analysis sets with the corresponding reason(s) for exclusion.

Note that additional analysis sets may be derived as part of sensitivity analyses.

2.3 Subgroup definitions

Sub-groups analyses may be included in exploratory and sensitivity analyses. Potential sub-groups:

- Randomisation Strata: Two treatment naïve eyes, one eye (first non-study eye) being treated with ranibizumab, and one eye (first non-study eye) being treated with an anti-VEGF other than ranibizumab.
- Age Group
- Sex
- Baseline BCVA group (≥ 70 letters, < 70 letters)
- Genotype sampling status
- Baseline lesion size
- Baseline IRF and/or SRF

Sub-group analyses may include descriptive analyses as well as forest plot(s) displaying treatment effects within each sub-group.

2.4 Assessment windows, baseline and post baseline definitions, missing data handling

Assessment windows to be applied to this study are detailed in Table 2.4-3.

Table 2.4-3 Study Assessment Windows

Period	Screen	Initial Treatment				Treatment Period			
		1	2	3	4	n	Month 12	n	Month 24 or Early Discontinuation
Weeks (relative to Baseline, Day 0)	-2 to 0	Baseline	4	8	v	52	v	104	
Visit window (days)			± 3	± 3	± 7	± 14	± 7	± 14	

n = number of visits as required per study protocol² section 5.5.4.1

v = variable. The number of visits will differ dependent on treatment interval as per study protocol³ section 5.5.4.1

2.4.1 Baseline and post-baseline definitions:

2.4.1.1 Baseline

Baseline is defined as the last available non-missing value collected just prior to the start of treatment in the study eye. Where a patient parameter value is missing for Visit 2:

1. If the patient has entered the treatment period (i.e. received at least one treatment), the baseline value for that patient will be imputed with the patient's Screening value.

2. If the patient never entered the treatment period, the baseline value will not be imputed.

Furthermore, patients with screening assessments, who do not enter the treatment period data, will only be included in data listings.

Note: Photography and FA performed no more than 14 days before the Baseline Visit will be accepted as the baseline examination (will not need to be repeated unless clinically indicated).

Note: BCVA performed no more than 2 days before the Baseline Visit will be accepted as the baseline examination. In addition, only BCVA data collected as per protocol (e.g. refracted ETDRS) will be accepted as the baseline examination.

2.4.1.2 Post-baseline

All assessments obtained after the date of first dose of study drug are considered as post-baseline unless otherwise specified. Missing data for post-baseline values, for example due to discontinuation, loss to follow-up, or other types of censoring (e.g. due to rescue medication), will not be imputed. Only subjects with measurements at any given time point will be included in the analysis for that given parameter and visit. Refer to Section 2.4.3 for further details regarding the handling of missing dates.

The study day for a baseline or post-baseline scheduled or unscheduled visit is defined as:

$$\text{Study day} = (\text{Date of visit}) - (\text{date of first treatment}) + 1$$

The study day for a scheduled or unscheduled visit before baseline is defined as:

$$\text{Study day} = (\text{Date of visit}) - (\text{date of first treatment})$$

2.4.1.3 Visit Windows

Output presented by visit will use a derived visit number, based on the number of weeks from Day 1; the derived visit number will be calculated using the actual visit date, as opposed to the scheduled visit date. Listings will also include the CRF nominal visit.

Visit names available will be 4-weekly for the first 12 weeks, and then fortnightly. For example: Week 4, Week 8, Week 12, Week 14, Week 16, Week 18, etc., with each visit having a visit window of ± 7 days.

Month 12 and Month 24 visits will be analysed using the CRF nominal visit window.

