Patients withdrawn from the study prior to completion of the 24 month assessment visit will be asked to return for an Early Discontinuation evaluation 30 days +/- 7 days following their last study visit.

SCN = Screening, BSL = baseline, INITIAL 3 TR. = Initial 3 treatments at 4 weekly intervals both arms, Flexible interval Tr = treatment intervals will differ based on arm and disease activity, Pr. EP = Primary Endpoint, EOS= End of study.

Figure 1 Study design

2 Project standards

Treatment groups for the analysis

The group labels for the 2 treatment groups for the analysis are: “Intensive” (Group I) and “Relaxed” (Group II).

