2.4.1.4 Early Discontinuation

The standard approach to handling Early Discontinuation visits will be to assign the visit to a derived visit number based on the date of termination. If the Early Discontinuation visit is assigned to a visit which already exists, then the assigned visit number will be set to the next visit.

Early Discontinuation visits may also be summarised as a separate distinct visit, in addition to, or in place of, the standard approach described in the paragraph above.

In addition, sensitivity analyses may be conducted to assess the impact of possible biases in endpoint analyses due to missing endpoint data for early withdrawal patients. These analyses may include Last Observation Carried Forward (LOCF), Baseline Observation Carried Forward (BOCF) and other imputation methods, as detailed further in Section 2.8.2.2.

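### The ±7-day visit windows in SAP 2.4.1.3 leave Days 37–49 and 65–77 with no derived visit and, from Week 12 on, put about one day in 14 in two visits with no tie rule

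*SAP*

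**What the plan says.** SAP Section 2.4.1.3 governs by-visit output: "Output presented by visit will use a derived visit number, based on the number of weeks from Day 1". It adds that "the derived visit number will be calculated using the actual visit date, as opposed to the scheduled visit date". The grid is "Visit names available will be 4-weekly for the first 12 weeks, and then fortnightly", and the same tolerance applies throughout: "Week 4, Week 8, Week 12, Week 14, Week 16, Week 18, etc., with each visit having a visit window of ± 7 days". There is one exemption: "Month 12 and Month 24 visits will be analysed using the CRF nominal visit window". Month 2 is not named.

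Four other places bear on this:

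- **Planned windows.** SAP Table 2.4-3 plans Weeks 4 and 8 at ±3 days, the variable visits at ±7 days, and Weeks 52 and 104 at ±14 days. It anchors on Baseline as Day 0, whereas the study-day formula in Section 2.4.1.2 makes first treatment Day 1.
- **Early withdrawal.** Withdrawn patients are "asked to return for an Early Discontinuation evaluation 30 days +/- 7 days following their last study visit" (SAP Section 1). Section 2.4.1.4 says the standard approach is to "assign the visit to a derived visit number based on the date of termination", moving to the next visit if that one is taken. This is the only collision rule in the SAP.
- **Second grid.** SAP Section 2.8.2.1 says the by-visit time course will be tabulated on a biweekly grid and mentions no 4-weekly start.
- **Uses of the label.** SAP Section 2.6 defines a visit interval as a difference of visit week numbers. Table 2.8.2.5-1 enters Visit as a categorical term, and Section 2.8.2.5 requires estimates at 2, 12 and 24 months.

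**The concern.** A visit-window rule should give every post-baseline day exactly one label. A ±7-day window spans 15 days, but the grid steps are 28 days and then 14 days. The windows are therefore too narrow for the first part and one day too wide for the second.

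A visit in a gap has no label and falls out of any table, figure or model indexed by derived visit. A visit on a shared day can be given either of two labels, so two programmers following the SAP can produce different outputs. The same label feeds the Section 2.6 interval summaries, which describe how the two regimens differ. An edge-day choice there moves an interval by two weeks.

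**Working it through.** **Inputs.** The grid, the ±7-day tolerance and the use of actual dates come from SAP 2.4.1.3. Day 1 as first treatment comes from 2.4.1.2, and the planned tolerances from Table 2.4-3.

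**Step 1: reproduce the grid.** Every 4 weeks to Week 12, then every 2 weeks, gives 4, 8, 12, 14, 16, 18, …. This matches the printed list and includes Weeks 52 and 104.

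**Step 2: windows.** The target day of Week w is 7w + 1, and the window is the target ± 7.

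| Visit | Target day | Window |
|---|---|---|
| Week 4 | 29 | 22–36 |
| Week 8 | 57 | 50–64 |
| Week 12 | 85 | 78–92 |
| Week 14 | 99 | 92–106 |
| Week 16 | 113 | 106–120 |
| Week 104 | 729 | 722–736 |

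**Step 3: gaps.** Spacing minus window length is 28 − 15 = 13 uncovered days between each 4-weekly pair: Days 37–49 and 65–77, so 13 + 13 = 26 days. Days 2–21 are also uncovered, but no visit is scheduled there.

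**Step 4: shared days.** On the fortnightly part 14 − 15 = −1, so each adjacent pair shares one day: 92, 106, …, 722. The count is (722 − 92)/14 + 1 = 46, or 1 day in 14 (about 7%). No day has more than two labels. Anchoring on Day 0 moves every figure down by one and leaves the pattern unchanged.

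**Step 5: Month 2.** The SAP does not state that Month 2 is the derived Week 8 visit; I assume it is.
- The planned window, 57 ± 3 = Days 54–60, lies wholly inside Days 50–64, and on this grid that window overlaps no other.
- A Week 8 visit 8 to 20 days late (Days 65–77) or early (Days 37–49) has no label. One further out takes the Week 12 or Week 4 label.

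**Step 6: can a visit inside its planned window be hit?** Assume intervals are counted from the actual previous visit.
- Week 8 three days early is Day 54. A 4-week interval gives 54 + 28 = 82, and ±7 gives Days 75–89. Days 75–77 have no label.
- Week 8 on time is Day 57. A 6-week interval gives 57 + 42 = 99, and ±7 gives Days 92–106. Both limits are shared days.

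**Step 7: effect on an interval.** Take visits at Week 8, Day 92 and Week 20 (Day 141). If Day 92 is called Week 12, the intervals are 4 and 8 weeks. If it is called Week 14, they are 6 and 6. The longest of these intervals changes from 8 to 6 weeks.

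**Step 8: early discontinuation.** Thirty ± 7 days after Baseline is Days 24–38; after an on-time Week 4 (Day 29) it is Days 52–66. In each case 2 of the 15 days (37–38 and 65–66) fall in a gap.

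**Step 9: the biweekly grid of 2.8.2.1.** Week 6 would cover Days 36–50 and Week 10 Days 64–78, which closes both gaps. Starting at Week 2, there would be 51 shared days. Two of them, Days 50 and 64, are the edges of the Week 8 window.

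**The case against.** The strongest reply is that Section 2.8.2.1 already implies a biweekly grid, on which the two gaps disappear, so the gap finding comes from reading 2.4.1.3 alone. That is a fair limit. But 2.4.1.3 lists the visit names explicitly and omits Weeks 6 and 10, so the SAP contains two grids, and the shared days survive under both.

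Several stronger readings are tempting, and the documents do not support them:

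- **That Month 2 data are broadly lost or ambiguous.** On the 2.4.1.3 grid Week 8 is never double-labelled, and a visit within its planned ±3 days is always labelled.
- **That the primary comparison is threatened.** Months 12 and 24 are taken from the nominal CRF visit.
- **That all fluid analyses suffer.** The endpoints on never resolving fluid count any visit up to the time point and need no label. Only point-in-time outcomes, such as no IRF and SRF at Month 2, could be affected.
- **That Table 14.1-5 in the Protocol document shows such visits will occur.** It is an empty shell with generic bins over the whole study. After Week 12 there are no gaps, so a late visit is still labelled.
- **That early withdrawals are especially likely to be lost.** Only 2 of 15 days are exposed in each case worked above, and Section 2.4.1.4 allows these visits to be summarised separately.

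Listings also keep the nominal visit, so nothing disappears from the record.

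**Conclusion.** The point stands as a defect in a stated rule. As written, 2.4.1.3 leaves 26 days between scheduled early visits without a label and gives two labels to 46 single edge days, about 1 in 14 from Week 12 on. No rule resolves either case, or two ordinary visits in one window. Visits inside their planned tolerance can be affected, provided intervals run from the actual previous visit.

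The reach is limited. It covers by-visit outputs, the Section 2.6 interval summaries (if their week number is the derived one) and any model that uses derived Visit. Month 2 is exposed only when Week 8 is 8 or more days off target, and the Month 12 and Month 24 labels are untouched. The documents give no distribution of visit dates, so the number of visits affected cannot be computed; the figures above are calendar days. The change should be made, but it does not bear on the Month 24 non-inferiority conclusion through the visit label.

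**What to change.** 1. Reconcile Section 2.4.1.3 with the biweekly grid in 2.8.2.1, and use one anchor (Day 0 or Day 1) throughout.
2. Replace the uniform ±7 days with contiguous, non-overlapping windows. For example, with first treatment as Day 1: Week 4 = Days 22–42 (or Days 2–42 if unscheduled early visits are to be labelled), Week 8 = Days 43–70, Week 12 = Days 71–91, then each fortnightly visit = target day −7 to +6 (Week 14 = Days 92–105, Week 16 = Days 106–119, and so on).
3. If two visits fall in one window, use the one nearest the target day, and the later one if they are equidistant. Make this consistent with the next-visit rule for Early Discontinuation in 2.4.1.4.
4. State that Month 2 is analysed by the nominal CRF Week 8 visit, as for Months 12 and 24.

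The cost is one SAP table and one change to the visit derivation. The downside is that some off-schedule early visits will be labelled further from their target day.

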2.4.1.4 Early Discontinuation

The standard approach to handling Early Discontinuation visits will be to assign the visit to a derived visit number based on the date of termination. If the Early Discontinuation visit is assigned to a visit which already exists, then the assigned visit number will be set to the next visit.

Early Discontinuation visits may also be summarised as a separate distinct visit, in addition to, or in place of, the standard approach described in the paragraph above.

In addition, sensitivity analyses may be conducted to assess the impact of possible biases in endpoint analyses due to missing endpoint data for early withdrawal patients. These analyses may include Last Observation Carried Forward (LOCF), Baseline Observation Carried Forward (BOCF) and other imputation methods, as detailed further in Section 2.8.2.2.

2.4.2 Study observation period

The study observation period for each patient will be defined as the period (in days) between the date of first treatment in the study eye (Day 1) and the date of the end of study visit + 1 (day).

2.4.3 Missing and implausible dates

The general approach to handling missing dates is shown below for dates of AEs, medical history diagnosis and concomitant treatment.

2.4.3.1 Adverse event start date imputation

AEs with completely missing onset dates will be considered to be treatment emergent. Adverse events with partially missing onset dates will also be included as treatment emergent when the month (if it exists) and the year occur on or later than the month and year of the initial study treatment date.

Partial AE start dates are imputed with reference to the treatment start date (TRTSTD) as outlined in the Imputation table below. Completely missing start dates will not be imputed.

For individual data listings, any missing or partial AE start dates will always be presented as recorded.

The date value is split into day, month, year sections and referenced in the Imputation table as outlined below:

	Day	Month	Year
Partial AE Start Date	Not used	MON	YYYY
Treatment Start Date (TRTSTD)	Not used	TRTM	TRTY

The following matrix explains the logic behind the imputation.

Comparison of Month Section	MON MISSING	MON<TRTM	MON=TRTM	MON>TRTM
YYYY MISSING	NC	NC	NC	NC
YYYY<TRTY	(D)=01JULYYYY Before Treatment Start	(C)=15MONYYYY Before Treatment Start	(C)=15MONYYYY Before Treatment Start	(C)=15MONYYYY Before Treatment Start
YYYY=TRTY	(B)=TRTSTD+1 Uncertain	(C)=15MONYYYY Before Treatment Start	(A)=TRTSTD+1 Uncertain	(A)=01MONYYYY After Treatment Start
YYYY=TRTY	(E)=01JANYYYY After Treatment Start	(A)=01MONYYYY After Treatment Start	(A)=01MONYYYY After Treatment Start	(A)=01MONYYYY After Treatment Start

The following table is the legend to the logic matrix.

Relationship	
Before Treatment Start	Partial date indicates AE start date prior to Treatment Start Date
After Treatment Start	Partial date indicates AE start date after Treatment Start Date
Uncertain	Partial date insufficient to determine relationship of AE start date to Treatment Start Date
Imputation Calculation	
NC / Blank Uncertain	No convention
(A) After Treatment Start or Uncertain	MAX(01MONYYYY,TRTSTD+1)
(B) Uncertain	TRTSTD+1
(C) Before Treatment Start	15MONYYYY
(D) Before Treatment Start	01JULYYYY
(E) After Treatment Start	01JANYYYY

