2.9.1 Adverse events

Adverse events (AEs) will be reported by primary system organ class and preferred term according to the Medical Dictionary for Regulatory Activities (MedDRA).

The MedDRA version used for reporting the study will be described in a footnote.

AEs will be deemed treatment emergent if the onset date is on or after the date of first study treatment. Any AEs recorded prior to the start of study treatment will be listed together with all other AEs. If any event has an incomplete onset date, this will be handled as described in section 2.4.3.1 above.

The incidence of treatment emergent AEs will be summarized separately for ocular and non-ocular AEs as follows:

- All AEs
- AEs by maximum severity
- AEs suspected to be related to study drug
- Serious AEs
- AEs leading to study treatment discontinuation

Patients who experienced multiple adverse events for a preferred term will be counted once, similarly for patients with multiple adverse events per system organ class.

All information pertaining to AEs noted during the study will be listed by patient, detailing AE (e.g., verbatim given by the investigator as well as the system organ class and preferred term according to MedDRA), date of starting and ending, severity, suspected relationship (by the investigator) to the study drug / ocular injection, and eye (for ocular events). The AE onset will also be shown relative (in number of days) to the day of (first) initial study treatment (ranibizumab injection) and relative (in number of days) to the Day 1.

The following AE listings will be provided:

- All adverse events,
- Ocular adverse events
- Adverse events suspected to be related to study drug and/or ocular injection.
- Serious adverse events,
- Adverse events leading to treatment withdrawal
- Adverse events leading to treatment interruption

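### The partial-date matrices in SAP 2.4.3.1 and 2.4.3.3 give two conflicting rows for the treatment-start year, and the AE rule ignores recorded stop dates

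*SAP*

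**What the plan says.** SAP 2.4.3.1 opens with a rule in text. A wholly missing onset is emergent: "AEs with completely missing onset dates will be considered to be treatment emergent". A partial onset is emergent "when the month (if it exists) and the year occur on or later than the month and year of the initial study treatment date".

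A matrix then assigns dates. Its four year rows are: year missing, `YYYY<TRTY`, `YYYY=TRTY`, and `YYYY=TRTY` again. The two rows with the same label differ:

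- Month missing: the first has "B)=TRTSTD+1 Uncertain", the second "E)=01JANYYYY After Treatment Start".
- Month before the treatment month: the first has "C)=15MONYYYY Before Treatment Start", the second "A)=01MONYYYY After Treatment Start".

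The legend evaluates code (A) as "MAX(01MONYYYY,TRTSTD+1)", the later of the first of the month and the day after first treatment.

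The matrix in 2.4.3.3 repeats the duplicate label. Its code (C) gives the day before or the day after first treatment, depending on the variable CMDTYP1C.

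Section 2.9.1 defines an emergent AE as one starting on or after first treatment and sends every incomplete onset back to 2.4.3.1. It provides for pre-treatment AEs: "Any AEs recorded prior to the start of study treatment will be listed together with all other AEs". It also lists AE end dates as data that will be shown. Nothing in 2.4.3.1 refers to the end date.

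**The concern.** These are operative rules. The AE incidence tables in 2.9.1 contain only treatment-emergent events, and the medication tables in 2.7 are split at the start of treatment. Two programmers following the printed matrices could give the same record different dates and put it on different sides of first treatment.

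The stop date is a separate matter. Where onset is uncertain, the text and the cells marked uncertain resolve the doubt towards emergent. A recorded end before the first injection removes that doubt, but the rule does not look at it. Such an event would be counted as emergent against data already in the database.

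**Working it through.** No sample size, power or event figure is involved, so the check applies the printed rules to example dates. The documents give no individual dates; a first treatment on 15 July 2014 is assumed, so TRTSTD+1 is 16 July 2014. Emergent means imputed onset on or after 15 July 2014 (2.9.1). Codes are evaluated by their legends.

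**AE matrix, onset year 2014**

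| Known month | First `YYYY=TRTY` row | Second `YYYY=TRTY` row | Text rule |
|---|---|---|---|
| Missing | 16 Jul 2014, emergent | 1 Jan 2014, labelled after, not emergent by date | Emergent |
| June (earlier) | 15 Jun 2014, not emergent | max(1 Jun, 16 Jul) = 16 Jul 2014, emergent | Not emergent |
| July (equal) | max(1 Jul, 16 Jul) = 16 Jul 2014, emergent | 16 Jul 2014, emergent | Emergent |
| August (later) | max(1 Aug, 16 Jul) = 1 Aug 2014, emergent | 1 Aug 2014, emergent | Emergent |

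Two of four cells conflict in date and status. The equal-month cell differs only in its label (uncertain versus after). The later-month cells agree. A start date of 10 March 2014 gives the same pattern. If the second row's cell text were used instead of the legend, the June and July cells would give 1 June and 1 July, both before treatment although labelled after.

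**Concomitant matrix, start year 2014**

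- Month missing: 14 July (CMDTYP1C 1 or 3) or 16 July (missing or 2), versus 1 January.
- Earlier month: 15 June versus 16 July.
- Equal month: 14 July versus 16 July when CMDTYP1C is 1 or 3; no difference when it is missing or 2.
- Later month: the rows agree.

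**Later years.** As printed, an AE onset in 2015 has no row and no imputed date. The text still classifies it. Read jointly, March 2015 is later than July 2014, so it is emergent. Read part by part, the year passes (2015 is after 2014) but the month fails (3 is less than 7), which would wrongly exclude it.

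**After relabelling the second row `YYYY>TRTY`.** Onsets in 2015 become 1 January (month missing), 1 March, 1 July and 1 September 2015. All are emergent, in line with the joint reading, and the conflict within 2014 disappears.

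**Stop date.** Take an AE with onset recorded as July 2014 and stop date 10 July 2014. Both rows impute 16 July 2014, so the event is emergent, with an imputed onset 16 − 10 = 6 days after its own recorded end. Relabelling does not change this.

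**The case against.** The strongest reply is that the duplicate label is a slip that corrects itself. Every cell of the second row is labelled after treatment and it uses 1 January, which makes sense only for a later year. The text rule also settles emergent status in both conflicting AE cells and, read jointly, for later years. Counting uncertain onsets as emergent is an inclusive convention applied alike to both arms. All of this is fair. It supports the relabelling and limits the consequences, but the matrix still contradicts itself as printed. An inclusive default for unknown timing does not justify overriding a known end date.

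A PDF-reading fault cannot be wholly excluded. However, `<` and `>` survive in the same tables' month headings, the label recurs in both matrices, and 2.4.3.2 prints a later-year branch.

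Several stronger readings are tempting and not supported:

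- *Later partial AE dates have no rule.* Only the imputed date is missing for later years; the text gives a status, and later months of the start year have a matrix rule.
- *Most of follow-up is affected.* If starts were spread evenly over a calendar year, (2 − 0.5)/2 = 75% of a 24-month follow-up would fall in later years. That is a share of time, not of partial dates or misclassified events.
- *Prior versus concomitant use rests on the matrix alone.* SAP 2.7 already classifies medications on start and end dates, although 2.4.3.3 sets out no end-date imputation.
- *Listings will show negative durations.* Section 2.4.3.1 keeps partial AE onsets as recorded in listings, and nothing says duration is computed from imputed dates.
- *Resolved screening events with partial onsets are known to exist.* Screening of up to two weeks (SAP Introduction) makes them possible; no document reports one.

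**Conclusion.** The point holds as a minor defect in two parts. First, both matrices print two different rows for the treatment-start year and none for later years. In the AE matrix two of four start-year cells conflict in substance and one in label only; in the concomitant matrix the equal-month cell can conflict as well. Second, 2.4.3.1 counts certain AEs as emergent without regard to a recorded stop date before first treatment. That comes mainly from the text and the first row's uncertain cells. The duplicate row adds false emergent status only for earlier months; for a missing month it works the other way.

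The cell comparison assumes the legends govern over the abbreviated cell text. The documents give no count of partial dates, so the number of affected records is unknown; it is probably small. AE and medication tables could change; the primary BCVA non-inferiority analysis does not depend on these rules.

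**What to change.** 1. In 2.4.3.1 and 2.4.3.3, change the label of the last matrix row to `YYYY>TRTY`.
2. In 2.4.3.1, reword the text rule as a joint comparison: a partial onset is emergent if its month and year, taken together as one calendar month, are the same as or later than those of first treatment; if only the year is known, compare years.
3. Add to 2.4.3.1: an AE whose known stop date is before the first treatment date is not treatment-emergent, whatever its onset, and no imputed onset may be later than the stop date.

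For medications the label correction is enough, given 2.7. The cost is two labels, one reworded sentence and one added sentence. No new data are needed, since AE end dates are already collected.
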